#### 4.2.3 End of Study

**Table 7** presents procedures for the end of study visit for all subjects. End of study visit will be performed when a subject discontinues study due to a confirmed PD, or a subject experienced an unconfirmed PD but is not eligible for a confirmation scan, or after 60 months of follow-up for subjects who achieve DC and remain disease free, or at the last study visit for subjects who discontinue study due to reason not related to PD.

Subjects who discontinue treatment due to any reason, including confirmed PD or initiation of alternative anticancer therapy, will be followed for survival according to the timepoints in **Table 6** (every 8 weeks up to 12 months post Cycle 1 Day 1, every 12 weeks from > 12 to ≤ 24 months, and every 6 months from > 24 to 60 months post Cycle 1 Day 1) unless the subject withdraws consent from further participation in the study. After 60 months, subjects may be contacted for survival every 12 months until the end of the entire study.

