#### 4.8.3      Efficacy

The final efficacy analyses will be based on the ITT Population defined in Section 4.8.1. Response will be summarized and compared between the experimental arm and control arm. Time-to-event data will be summarized using the Kaplan-Meier estimates. The following efficacy endpoints will be analyzed. Each experimental arm will be compared to the control arm. There will be no formal comparisons between any experimental arms. RECIST v1.1 will be used as primary analysis for all endpoints when applicable. Localized post-radiation changes which affect lesion sizes may occur and there may be high levels of necrosis/fibrosis with little or no active tumor in recently irradiated lesions. However, accepting these limitations in this patient population with prior curative radiation, treatment the prior irradiated lesions may be considered measurable and selected as target lesions providing they fulfill the other criteria for measurability. More details will be provided in the statistical analysis plan.

- Best overall response (BOR), defined as the best response (in the order of complete response [CR], PR, SD, PD, and not evaluable) among all overall responses recorded from randomization until progression, or the last evaluable disease assessment in the absence of PD prior to the initiation of subsequent anticancer therapy or discontinuation from the study, whichever occurs first. The BOR of CR or PR must be confirmed, which means a response of CR/PR is recorded at 1 visit and confirmed by repeat imaging not less than 28 days (4 weeks) after the visit when the response was first observed with no evidence of progression between the initial and CR/PR confirmation visit.
- OR, defined as BOR of confirmed CR or confirmed PR according to RECIST v1.1.
- DC, defined as BOR of confirmed CR, confirmed PR, or SD based on RECIST v1.1. Disease control rate (DCR) at 16 weeks is defined as a BOR of confirmed CR, confirmed PR or having SD with duration of SD lasting 16 weeks.
- DoR, defined as the time from the first documentation of a subsequently confirmed OR to the first documentation of a disease progression according to RECIST v1.1 or death due to any cause, whichever occurs first. Only subjects who have achieved OR (confirmed CR or confirmed PR) will be evaluated for DoR.

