- PFS, defined as the time from randomization until the first documentation of disease progression according to RECIST v1.1 or death due to any cause, whichever occurs first, regardless of whether the subject receives subsequent anticancer therapy prior to progression. Subjects who are alive progression free at the time of DCO will be censored on the date of their last evaluable tumor assessment. PFS-12 will be estimated using the Kaplan-Meier method.

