### **3.4.2.2 Duration of Response**

Duration of response (DoR) is defined as the time from the first documentation of a subsequently confirmed OR until the first documentation of a disease progression or death due to any cause, whichever occurs first, regardless of whether the subject receives subsequent anticancer treatment prior to progression. Only subjects who have achieved OR (confirmed CR or confirmed PR) will be evaluated for DoR. DoR is defined in months as follows:

$$\text{DoR (months)} = (\text{Date of PD/death or censoring} - \text{Date of first confirmed disease response} + 1) / (365.25/12)$$

The date of PD/death or censoring is the same as defined for PFS in Section 3.4.2.4. The median DoR and its 95% CI will be estimated using the Kaplan-Meier method.

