### **3.4.2.4 Progression-free Survival**

Progression-free survival (PFS) is defined as the time from randomization until the first documentation of a disease progression or death due to any cause, whichever occurs first, regardless of whether the subject receives subsequent anticancer treatment prior to progression. Subjects who have no documented progression and are still alive at the time of analysis will be censored at the time of the latest date of assessment from their last evaluable RECIST v1.1 assessment. PFS is defined in months as follows:

$$\text{PFS (months)} = (\text{Date of PD/death or censoring} - \text{Date of randomization} + 1) / (365.25/12),$$

The censoring guidance and the date of PD/death or censoring are given in the table below. The number and percentage of subjects experiencing a PFS event and Kaplan-Meier plots of PFS will be presented by treatment group. The median PFS and its 95% CI will be estimated using the Kaplan-Meier method. The proportion of subjects progression-free and alive at 12

months (PFS-12) and associated 95% CI will be estimated using the Kaplan-Meier method. Additional PFS landmarks to be included in the final analysis are PFS-18, PFS-24, and PFS-36.

The difference in PFS between each experimental arm and control arm will be tested for significance by using a stratified log-rank test on histology (adenocarcinoma vs non-adenocarcinoma). The log-rank test will be carried out with the Breslow method for handling ties. The hazard ratio (HR) (experimental vs. control) with two-sided 95% CI will be estimated by stratified Cox regression model on histology with ties handled by the Efron method ([Efron et al, 1977](#)).

The comparison of PFS-X (X=12, 18, 24, 36 months) between each experimental arm and control arm will be performed by normal approximation under complementary loglog (cloglog) transformation ([Klein et al, 2007](#)). The test statistic shown below asymptotically follows a chi-square distribution with one degree of freedom under the null hypothesis  $H_0: S_1(t) = S_2(t)$ .

$$X^2 = \frac{\left( \log(-\log(\hat{S}_1(t))) - \log(-\log(\hat{S}_2(t))) \right)^2}{\hat{\sigma}_1(t)^2 / \left( \log(\hat{S}_1(t)) \right)^2 + \hat{\sigma}_2(t)^2 / \left( \log(\hat{S}_2(t)) \right)^2}$$

where

- $\hat{S}_k(t)$ , with  $k = 1, 2$  is the Kaplan-Meier estimate of the survival function for the  $k$ th treatment group

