**Table 3.4.1      Summary of Censoring Guidelines for PFS**

Situation	Date of PD/Death or Censoring	PFS Outcome
Documented Progressive Disease (PD) or death	Date of earliest sign of PD or death, whichever comes first	Event (unless the censoring rule specified below)
Death or PD immediately after $\geq 2$ consecutive missed or non-evaluable disease assessments as per the protocol specified assessment schedule	Date of last progression-free disease assessment prior to missed or non-evaluable assessments, or randomization, whichever occurred last	Censored
No PD or death at time of analysis or lost to follow-up	Date of last evaluable progression-free disease assessment	Censored
No tumor assessment at baseline and no evidence of PD at first post-baseline disease assessment OR No tumor assessment post-first dose, and no death prior to second scheduled post-baseline disease assessment	Date of randomization	Censored

PD = progressive disease; PFS = progression-free survival.

Subjects having missing lesion data at baseline or no disease assessments post-first dose of IP will have PFS censored at the date of randomization unless the subject dies prior to the second scheduled post-baseline disease assessment in which case the death date will qualify as a PFS event.

If a subject has two or more consecutive completely missed or non-evaluable assessments followed immediately by death or an assessment showing radiologic disease progression, then the subject will be censored for PFS. PFS will be censored at the date of randomization or the last progression-free disease assessment prior to the missed or non-evaluable assessments, whichever occurred last.

If a subject has two or more consecutively missed or non-evaluable assessments followed by an assessment showing no radiologic disease progression, then the assumption will be that the subject did not progress during the missed or non-evaluable assessments.

The length of gap (in number of days) to determine two or more consecutive assessments is defined as the following:

- 126 days during the first 12 months (A 8-week disease assessment interval plus a 7-day window for each assessment).

- 182 days from month 12 to month 24 (A 12-week disease assessment interval plus a 7-day window for each assessment).
- 422 days after month 24 (A 6-month disease assessment interval plus a 4-week window for each assessment).

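### SAP 3.4.2.4 censors some documented PFS events that protocol 4.8.3 counts, and no PFS or DoR analysis under the protocol definition is clearly planned

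*SAP*

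**What the plan says.** **Protocol 4.8.3, PFS.** The event is progression per RECIST v1.1 or "death due to any cause, whichever occurs first, regardless of whether the subject receives subsequent anticancer therapy prior to progression". The only censoring rule is: "Subjects who are alive progression free at the time of DCO will be censored on the date of their last evaluable tumor assessment". There is no exception for missed assessments.

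**Protocol 4.8.3, DoR.** Duration ends at "disease progression according to RECIST v1.1 or death due to any cause, whichever occurs first. Only subjects who have achieved OR". No censoring rule is stated for DoR.

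**SAP 3.4.2.4, opening definition.** This repeats the protocol's event definition and its condition for censoring: "Subjects who have no documented progression and are still alive at the time of analysis will be censored". It then sends the reader to Table 3.4.1 for the censoring guidance.

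**SAP 3.4.2.4, Table 3.4.1 and the text below it.** The first row makes PD or death an event unless a later censoring rule applies. The second row and the text give that rule for two or more consecutive missed or non-evaluable assessments: if these are "followed immediately by death or an assessment showing radiologic disease progression, then the subject will be censored for PFS". The date is moved back: "PFS will be censored at the date of randomization or the last progression-free disease assessment prior to the missed or non-evaluable assessments", whichever is later. A companion rule censors at randomization a subject with no assessment after the first dose, unless death comes before the second scheduled assessment.

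**SAP 3.4.2.2, DoR.** "The date of PD/death or censoring is the same as defined for PFS".

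**Follow-up.** Under protocol 4.1.6, protocol-specified assessments end when a subject starts alternative treatment. Under protocol 4.2.3, "Subjects who discontinue treatment due to any reason, including confirmed PD or initiation of alternative anticancer therapy, will be followed for survival", unless consent is withdrawn.

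**The concern.** A subject known to have died, or to have progressed on a scan, can be censored in the SAP's PFS analysis although the protocol's definition makes that subject an event. This does more than fill in detail, because it alters the set of events.

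The follow-up scheme gives the rule something to act on. A subject who starts new therapy without documented PD leaves the scan schedule but stays in survival follow-up. If that subject later dies, the death will tend to fall after a two-scan gap. The protocol keeps the event regardless of later therapy; the SAP rule can remove it. The SAP also does not say whether scans that are no longer required count as missed. The second row of Table 3.4.1 refers to the protocol's assessment schedule, while the gap lengths in days make no exemption, so the programmer would have to choose.

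At stake are PFS (stratified log-rank test, Cox hazard ratio and subgroup hazard ratios), the landmarks PFS-12, -18, -24 and -36, and DoR. If subjects stop scans because they are deteriorating, censoring them at the last clean scan is informative. The study is open-label, so stopping could differ between arms.

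**Working it through.** **1. Trigger lengths.** The SAP's gaps follow from 2 × (interval + window):

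- first 12 months: 2 × (56 + 7) = 126 days
- months 12 to 24: 2 × (84 + 7) = 182 days
- after month 24: 2 × (183 + 28) = 422 days, taking 6 months as 183 days

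All three match the SAP.

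**2. One subject under both rules (invented dates).** Last clean scan on day 168 after randomization, scans due on days 224 and 280 missed, death on day 300. The gap is 300 − 168 = 132 days, which exceeds 126. With the SAP formula (days + 1)/(365.25/12):

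- protocol definition: event at 301/30.4375 = 9.9 months
- SAP rule: censored at 169/30.4375 = 5.6 months

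The subject counts against PFS-12 under the first rule and not under the second.

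**3. Inputs for the size.** From the documents: 60 subjects per experimental arm (SAP 2.4); durvalumab median PFS of 17.2 months in the earlier Phase 3 study (protocol 1.1); scans every 8 weeks to month 12, every 12 weeks to month 24, then every 6 months (protocol Tables 5 and 6). Assumed: exponential PFS, 36 months of follow-up, and a share f of events that follow a two-scan gap. The documents give no figure for f, so a range is shown.

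**4. Baseline by hand.** The last scan within 36 months falls at 34.1 months, so events per 60 = 60 × (1 − 2^(−34.1/17.2)) = 44.8. The last scan before month 12 falls at 11.0 months, so PFS-12 ≈ 2^(−11.0/17.2) = 64%. The simulation (100,000 subjects) agrees.

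**5. Effect of the SAP rule.**

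| f | Events per 60, protocol | Events per 60, SAP | PFS-12, protocol | PFS-12, SAP |
|---|---|---|---|---|
| 5% | 44.9 | 42.6 | 64.0% | 65.2% |
| 10% | 44.8 | 40.3 | 64.0% | 66.4% |
| 15% | 44.8 | 38.2 | 64.2% | 67.8% |
| 20% | 44.8 | 35.7 | 64.1% | 69.2% |

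The loss is 2.3 to 9.1 events, and PFS-12 rises by 1.2 to 5.1 points.

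**6. Hazard ratio with no true effect (20,000 per arm).**

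| f, control v experimental | HR, protocol | HR, SAP |
|---|---|---|
| 5% v 5% | 1.01 | 1.01 |
| 10% v 10% | 1.00 | 1.00 |
| 5% v 10% | 1.01 | 0.97 |
| 5% v 15% | 1.02 | 0.94 |
| 5% v 20% | 0.99 | 0.88 |
| 10% v 20% | 1.00 | 0.91 |

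**7. A simplification that overstates the upper end.** The share f was applied to all events, but an event at the first or second scan cannot follow two missed scans. Events by the second scan (3.7 months) number 60 × (1 − 2^(−3.7/17.2)) = 8.3 per 60, which leaves 44.8 − 8.3 = 36.5 eligible. If f is the share of those only, the loss is 0.05 × 36.5 = 1.8 to 0.20 × 36.5 = 7.3 events, and the shifts in PFS-12 and HR shrink too. The 20% figures are best read as ceilings.

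**The case against.** **The exception is signposted.** SAP 3.4.2.4 points to the table, and the table's first row says a later rule may override it. A reader might infer that the SAP contradicts itself by accident. It does not: general rule and exception are laid out, and apart from scans no longer required, a programmer has one operative instruction. This stands.

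**The protocol defers to the SAP.** Protocol 4.8.1 and 4.8.3 both leave further detail to the SAP, and censoring after two missed visits is a common convention. So it is too strong to say that nothing in the protocol allows the rule. What remains is that recoding events goes beyond detail, and the SAP's version history does not list it as a departure.

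**The deaths are not lost.** A reader might infer that every such death is known and thrown away. Follow-up ends if consent is withdrawn, and captured deaths still count in OS. They are recoded for PFS and DoR only.

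**DoR is a narrower case.** The protocol's alive-only censoring sentence belongs to PFS. For DoR the mismatch rests on the event definition alone.

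**The protocol rule is not clearly better.** It censors scan-stoppers who stay alive at their last scan but counts those who die at a possibly much later date. A separate simulation (6,000 per arm, post-progression median 9 months) assumed progression unimaged in 5% of control and 20% of experimental subjects, with a true HR of 1.01. The protocol rule gave 0.97 and the SAP rule 0.92; experimental PFS-36 was 27.1% and 29.4% against a true 23.2%. Both are biased. When scan stopping was unrelated to disease (10% v 25% per year), the HRs were 1.08 (protocol) and 1.06 (SAP). If no true effect applied there too, the SAP rule was slightly nearer. So the choice of main rule is a trade-off.

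**The effect is small against sampling error.** With about 45 events per arm, the SE of log HR is √(2/45) = 0.21. Even 0.88 lies only 0.13/0.21 = 0.6 SE from 1.

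**Other analyses may cover it.** SAP 3.4.3 and Appendix 7.1 present investigator-reported outcomes without censoring rules, but name no PFS or DoR analysis. The sensitivity analyses in SAP 3.3.5 and 3.4.1.2 are optional and concern the primary analysis. None clearly supplies the protocol-defined result.

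**Conclusion.** The protocol and the SAP's operative rule count different PFS events, DoR inherits the difference, and no analysis under the protocol definition is clearly planned. That follows from the texts and needs no assumption.

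The size does rest on assumptions. For 5% to 20% of events after a two-scan gap, about 2 to 9 of about 45 events per 60 subjects are censored and PFS-12 rises by about 1 to 5 points, with the upper ends as ceilings.

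A reader might go further and infer that the rule favours the experimental arms. The documents do not support that: they give no missed-scan rates by arm, and equal shares leave the HR at about 1.0. Nor do they show that the protocol rule must be the main analysis.

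PFS and DoR are secondary, and the sample size was not set for power or Type I error. The primary ORR analysis is unaffected, as are the Go/No-Go decisions, which use ORR and DCR. This is an inexpensive correction that should be made, not a threat to the trial's main conclusion.

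**What to change.** 1. Reconcile protocol 4.8.3 and SAP 3.4.2.4 on which rule is the main one for PFS and DoR, and record the reason.
2. Whichever is chosen, prespecify the other as a named sensitivity analysis for PFS, each PFS landmark and DoR, so that the protocol-definition result is always produced.
3. State whether scans no longer required after alternative therapy count as missed.
4. Report by arm how many PDs and how many deaths change status between the two rules.

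The cost is revised wording, one extra run of the PFS and DoR programs, and a second PFS figure to explain.

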| Serum chemistry                     | X                    | X d                                     | X                        | X                        | X                        | X  |
| Hematology                          | X                    | X d                                     | X                        | X                        | X                        | X  |
| Urinalysis                          | X                    | As clinically indicated                            |                          |                          |                          |  |
| Thyroid function tests e | X                    | X d                                     | X                        | X                        | X                        | X  |
| Pregnancy test f         | X                    | X  | X                        | X                        | X                        | X  |
| Coagulation parameters              | X                    |  |                          |                          |                          |  |
| Hepatitis B and C; HIV g | X                    |  |                          |                          |                          |  |
| Concomitant medications             | X                    | X  | X                        | X                        | X                        | X  |
| Assessment of AEs/SAEs              | X                    | X  | X                        | X                        | X                        | X  |
| Disease assessment (scans)          | X h       |  |                          | X
(within 7 days)     |                          | Cycle 5 then every 2 cycles
(within 7 days) |

**Table 5** Schedule of Screening and Treatment Period Procedures

| Procedure                              | Screening         | Treatment Period: Up to 12 Months
28-day Cycles |                          |                          |                          |   |
|--|-------------------|--|--------------------------|--------------------------|--------------------------|---|
|  |                   | Cycle 1  | Cycle 2                  | Cycle 3                  | Cycle 4                  | Cycle 5 through Cycle 13                            |

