#### 4.2.2 Follow-up Period

**Table 6** presents follow-up procedures for subjects who completed study treatment and maintain DC, subjects who discontinued study treatment due to other reason not related to PD (Section 4.1.6), and subjects who experienced unconfirmed PD and are eligible for a confirmation scan. Procedures for subjects who discontinue study treatment due to PD are provided in Section 4.2.3. Overall, all subjects continuing in the study must adhere to the study procedures for up to 5 years (from randomization) provided they achieve DC and remain disease free.

As OS is a late endpoint in this patient population, after the planned 5-year post randomization study period, subjects may be contacted for survival every 12 months.

**Table 6 Schedule of Follow-up Procedures: Subjects Who Completed Study Treatment and Maintain DC, Subjects Who Discontinued Study Treatment Due to Other Reason Not Related to PD, and Subjects Who Experienced Unconfirmed PD and are Eligible for a Confirmation Scan**

| Time since Cycle 1 Day 1                    | ≤ 12 Months                          | > 12 to ≤ 24 Months               | > 24 to 60 Months             |
|---|--------------------------------------|-----------------------------------|-------------------------------|
| Follow-up based on previous scheduled visit | Every 8 Weeks
(± 3 days)          | Every 12 Weeks
(± 7 days)      | Every 6 Months
(± 4 weeks) |
| Procedure                            |                                      |                                   |                               |
| Physical examination                        | X                                    | X                                 | X                             |
| Vital signs                                 | X                                    | X                                 | X                             |
| ECOG performance status                     | X                                    | X                                 | X                             |
| Serum chemistry                             | X                                    | X                                 | X                             |
| Thyroid function tests a         | X                                    | X                                 | X                             |

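### PFS censoring: the 126-, 182- and 422-day gaps do not reproduce the SAP's own two-missed-scans rule where the scan interval changes at months 12 and 24

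*SAP*

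**What the plan says.** SAP 3.4.2.4 states the rule twice as a count. Table 3.4.1 censors death or PD that directly follows two or more "consecutive missed or non-evaluable disease assessments as per the protocol specified assessment schedule". The text under the table applies to a subject with "two or more consecutive completely missed or non-evaluable assessments followed immediately by death" or by a scan showing progression. In both places PFS is censored at the last progression-free assessment before the gap, or at randomization if later.

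The same section then converts the count to days: "The length of gap (in number of days) to determine two or more consecutive assessments is defined as the following". The limits are 126 days in the first 12 months, "182 days from month 12 to month 24", and "422 days after month 24 (A 6-month disease assessment interval plus a 4-week window for each assessment".

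On treatment, Protocol Table 5 schedules scans at Cycle 3, then "Cycle 5 then every 2 cycles" to Cycle 13. Protocol 4.2.3 gives the later follow-up times as "every 12 weeks from > 12 to ≤ 24 months, and every 6 months from > 24 to 60 months". Table 6 counts time from Cycle 1 Day 1 and spaces visits by "Follow-up based on previous scheduled visit". SAP 3.4.2.2 takes the DoR event and censoring dates from the PFS rule.

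**The concern.** The three limits fit a schedule with one constant interval, but the protocol's interval goes from 8 to 12 weeks and then from 12 weeks to 6 months. A gap that spans a change has one short and one long interval, and the SAP has no limit for it. The SAP also does not say whether the phrases about months refer to the last scan, the missed scan or the event, nor whether months run from randomization (as PFS does) or from Cycle 1 Day 1 (as Table 6 does).

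The same subject can therefore be an event under the table and censored under the day limit, or the reverse. That affects the PFS landmarks beyond month 12 and DoR, through a programming choice that the SAP leaves open.

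**Working it through.** **1. The SAP's limits reproduce.** Limit = 2 × (interval + window):
- 2 × (56 + 7) = 126
- 2 × (84 + 7) = 182
- 2 × (183 + 28) = 422, taking 6 months as 183 days

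**2. Scan calendar.** With Cycle 1 Day 1 as day 1 and 28-day cycles, on-treatment scans fall on days 57, 113, 169, 225, 281 and 337 (weeks 8 to 48). After that Tables 5 and 6 do not fix the days. At month 12 the next scan may be 12 weeks later (day 421) or 8 weeks later (day 393). At month 24 the first step past the boundary may be 6 months or 12 weeks. That gives four calendars:
- A: 12 weeks, then 6 months (421, 505, 589, 673, 856)
- B: 8 weeks, then 12 weeks (393, …, 729, 813, 996)
- C: 12 weeks, then 12 weeks (421, …, 673, 757, 940)
- D: 8 weeks, then 6 months (393, …, 729, 912)

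**3. Count against day limit.** The SAP gives no operator, so I take a gap greater than the limit as censored. Examples on calendar A:

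| Last scan → PD | Scans missed | Gap (days) | Table 3.4.1 | Limit by last scan | Limit by first missed scan | Limit by PD date |
|---|---|---|---|---|---|---|
| 281 → 421 | 1 | 140 | event | 126: censored | 126: censored | 182: event |
| 337 → 505 | 1 | 168 | event | 126: censored | 182: event | 182: event |
| 589 → 856 | 1 | 267 | event | 182: censored | 182: censored | 422: event |
| 505 → 856 | 2 | 351 | censored | 182: censored | 182: censored | 422: event |

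No column of limits agrees with the table in every row. On the PD-date reading the month-12 change is handled correctly at nominal dates, unless there is a week-56 scan (225 → 393 = 168 < 182 with two missed). Deaths can also escape on that reading. After a last scan on day 281, a death 148 to 182 days later follows two missed scans but is kept; after day 589 the range is 296 to 422 days.

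Away from the changes, limits and count agree for PDs found at scheduled scans.

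**4. Size.** The documents give no miss rate or follow-up time. Assumptions: exponential PFS with a 17.2-month median (the durvalumab figure in Protocol 1.1), 48 months of follow-up, scan dates uniform within their windows, and 10% of scans missed. Simulated change in PFS-36 against the count rule, in percentage points:

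| Reading | A | B | C | D |
|---|---|---|---|---|
| Last scan, at least one scan missed | +2.3 | +1.0 | +1.8 | +1.2 |
| First missed scan | +1.0 | +0.1 | +0.5 | +0.6 |
| PD date | −0.1 to −0.3 over the four calendars | | | |

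PFS-12 moves by less than 0.2 point in every case. On the last-scan reading PFS-24 moves by up to about 1 point. With a true HR of 1.0 or 0.65 and 15% of events as deaths, the HR shifts by at most 0.004 and the between-arm PFS-36 difference by at most 0.4 point.

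For scale, exponential PFS gives 0.5^(36/17.2) = 0.234 at 36 months. A binomial approximation with 60 subjects has a 95% half-width of 1.96 × √(0.234 × 0.766/60) = 0.107, about 11 points.

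**5. Limits that would match.** Apply the SAP's own terms to the next two intervals actually scheduled after the last scan. On calendar A:
- day 281: 63 + 91 = 154
- day 337: 91 + 91 = 182
- day 589: 91 + 211 = 302
- day 673: 211 + 211 = 422

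The widest one-missed gaps just meet the two mixed limits: 140 + 7 + 7 = 154 and 267 + 7 + 28 = 302. So the operator matters: with > these stay events, with ≥ they do not.

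**The case against.** **Silence rather than contradiction.** The limits can be read as covering only gaps inside one period, so that the table's count applies to a gap that crosses a change. That reading is reasonable, but the SAP does not state it, and the text makes the day gap the means of determining the count. A programmer following it would use days.

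**The programming plan may settle it.** SAP section 1 refers to a statistical programming plan, which is not among the documents and may name the date. Each of the three natural dates still leaves mismatches with Table 3.4.1.

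**One phrase would nearly do.** Naming the PD or death date brings the effect close to zero: 0.2 to 0.4% of subjects misclassified with 10% of scans missed. This stands, and it is a reason to rate the point low. It does not make the limits agree with the table.

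**The size should not be overstated.** A reader might infer a shift of about 5 points in PFS-36, half of the confidence half-width. That figure arises on the last-scan reading with calendar A, and only if a PD found on time with no missed scan is also censored (673 → 856 = 183 > 182). The SAP's condition of completely missed or non-evaluable assessments excludes this.

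**The endpoint effect is limited.** PFS-12, the only PFS landmark among the protocol's endpoints, barely moves. PFS-36 is an additional landmark in the SAP. This also stands.

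**Conclusion.** The point holds and is minor. At the two interval changes the day limits do not reproduce Table 3.4.1's count under any of the three candidate selecting dates. That part rests only on the SAP and protocol schedules, on taking a gap greater than the limit as censored, and on a calendar compatible with Tables 5 and 6.

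The size is less certain. PFS-36 moves by about 0 (PD-date reading) to about +2 points (last-scan reading with at least one missed scan), at most roughly one fifth of its half-width. This depends on the assumed 10% miss rate, the exponential PFS, the follow-up time and the scan calendar. DoR inherits the same dates; its shift was not quantified.

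A reader might also infer a biased treatment comparison or a threat to the primary result. The documents do not support either: the rule is the same in all arms, the simulated HR and between-arm shifts are negligible, and ORR does not use this censoring rule.

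**What to change.** State in SAP 3.4.2.4 that the count of missed or non-evaluable protocol-scheduled assessments governs. List the nominal scan days used for that count across months 12 and 24, with the sponsor confirming the calendar. State whether months run from randomization or from Cycle 1 Day 1.

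If day limits are kept, name the date that selects the limit and the operator (> or ≥). For a gap that crosses a change, use the sum of the two (interval + window) terms scheduled next after the last progression-free scan, for example 154 and 302 days in place of a single-period limit. A narrow grey zone for deaths just after the second missed window closes would remain; the count rule avoids it. One confirmed calendar is enough, so limits for every conceivable calendar are not needed.

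The cost is one SAP paragraph and a small programming change, with no new data.
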